Participants will be Latino community-dwelling adults with pre-diabetes as defined by HbA1c of 5.7-6.5% and BMI of 25-45 kg/m². Participants will be recruited and pre-screened from a variety of Latino community settings. Screening activities will be conducted at churches and other community settings, with baseline and follow-up visits occurring in the Clinical Research Unit (CRU) of Wake Forest Baptist Medical Center or other WFBH facilities, including Lexington Medical Center, as needed. Following baseline assessment, participants will be randomized to one of the treatment conditions described above. Follow-up exams will occur every 6 months to assess weight, laboratory parameters, and other measures of the intervention effect. Due to the nature of the lifestyle intervention, neither participants nor project personnel can be masked to the participant's intervention status; however, personnel performing laboratory tests and interpreting their results will be masked. The project will operate under the general oversight of the Maya Angelou Center for Health Equity and will use an external safety officer to monitor trial progress and participant safety.

B. Conceptual Framework

The proposed study is guided by a conceptual model that integrates key concepts from social cognitive theory and the literature surrounding group dynamics^{20,21}. Weight loss and fitness improvement achieved through a combination of modifying eating and physical activity behaviors is determined by the joint, reciprocal interaction of personal factors (e.g., beliefs and values), social influences (e.g., support and strain), and features of the physical environment (e.g., structure and access to resources). The lifestyle intervention incorporates several components of social cognitive theory: self-efficacy, outcome expectations, and incentives.

Self-efficacy refers to the extent to which individuals believe they can successfully perform specific behaviors, even when confronted with barriers. Research has shown that self-efficacy beliefs are determined by prior behavior, physical symptoms (e.g., pain, fatigue), appetite, affect, and environmental/social factors. Because self-regulatory behaviors are important to successful behavior change, the intervention is designed to increase self-efficacy in relation to goal setting, self-monitoring, and other self-management skills.

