Potential participants who 1) satisfy the inclusion/exclusion criteria previously described, and 2) provide a signed informed consent will be invited to the CRU or Lexington Medical Center to complete a baseline visit and be randomized to one of the treatment conditions. The number of participants recruited and randomized during a given month will vary, depending both on the flow of interested participants into the screening process and the needs/limitations of the lifestyle intervention arm of the study. We anticipate LHA-led intervention groups of 10-15 participants and for the intervention to begin within one month of randomization. We will recruit participants in waves to ensure that there are sufficient numbers to fill intervention groups. We will adopt a permuted block design with varying block size, as this can lower the time randomized individuals wait for intervention groups to develop and ensure a degree of balance. A list of random study arm assignments will be generated and used by the web based randomization routine to make sequential assignments. Randomization will occur in a 2:1 pattern; for every two participants randomized to the lifestyle intervention, one will be randomized to the usual care group. Table 2 illustrates that the 225 participants will be recruited in 11 distinct waves with 20-21 in each wave. We anticipate the recruitment period lasting from the latter part of Year 1 through Year 3. Based on our 2:1 randomization, approximately 14 participants will be randomized to the intervention condition in each wave. We anticipate a total of 11 LHA-led groups.

Table 1. Planned Recruitment for La Comunidad

Months	Year 1		Year 2		Year 3	
	1-6	7-12	1-6	7-12	1-6	7-12
Waves		Wave 1	Waves 2-4	Waves 5-6	Waves 7-9	Waves 10-11
Number of Participants		21	61	41	61	41
					Total	225

F. La Comunidad Lifestyle Weight Loss Intervention

a. Goals of the Lifestyle Intervention

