All statistical analyses will be conducted by the Research Core of the Maya Angelou Center for Health Equity. The main hypothesis being tested involves evaluating the mean differences in changes in HbA1c at one year. Secondary outcomes include changes in clinical characteristics and biochemical lab results and biomarkers of insulin sensitivity. Statistically, all of these analyses could be treated in a similar fashion after appropriate transformations are made to satisfy assumptions made about the distribution of residuals. We will apply a repeated measures analysis of variance to changes (collected across the planned visits at 6, 12, 18, and 24 months) to address intra-individual correlations, which accommodates interim testing and allows participants with incomplete patterns to contribute to the analysis and evaluation²⁴. Our analysis adopts the intention-to-treat approach. Inference for primary comparisons will be two-sided, with significance level alpha = 0.05. We will use repeated measures analysis of covariance in which indicators for visit are included to control for systematic temporal differences that may occur that are common to both intervention conditions. We test differences from baseline (rather than using baseline levels as a covariate in analyses of post-randomization values), as it is these differences that are the focus of our intervention and to limit the bias associated with estimates from regression models that include fallible covariates. Random effects terms will be used to model differences as these have been shown to yield inferences of more appropriate size than fixed effect models. Compound symmetry models will be used to model intra-subject

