longitudinal covariance and models will be fitted via maximum likelihood. The primary comparison will be based on a Wald statistic. We will not include additional covariates or stratification in the primary comparison, however, we will describe any chance differences between cohorts and, in supporting analyses, covary comparisons on any baseline factors that appear to be unbalanced. When we are developing the ANCOVA models, we will determine whether the assumptions of general linear models are satisfied. Diagnostics and residual plots will be reviewed to ensure that the assumptions are met. Should assumptions be violated, transformations of the outcome data will be considered: the order of the priority in choosing a transformation will be to satisfy the (1) linearity assumption, (2) homogeneity assumption (homoscedasticity), and (3) normality assumption. As mentioned above, secondary (supporting) analyses will assess the influence of covariates on the mean differences and to explore whether mean differences vary over follow-up time (using interaction terms). In addition, we will explore the homogeneity of LHAs with respect to outcome measures using hierarchical mixed models in which LHAs are coded as random effects and participant data are nested within LHAs. Such models will allow us to place confidence bounds on the contributions of LHA differences to overall variability.

Sample Size and Power

In this section we justify our plans to recruit and follow 225 participants who will be randomized with equal probability to either the intensive lifestyle intervention or individual education arm. Our goal is to provide greater than 80% statistical power to detect an average difference of .25 standard deviations from baseline in HbA1c between the two groups at one year. With a sample size of 225 participants, we will have 85-88% power to detect a net intervention effect of .25%. These estimates include allowance for a 5% loss to follow-up rate every 6 months. Although the DPP has not published any data that allow us to estimate the standard deviation and longitudinal correlation of HbA1c, similar studies conducted for a longer period of time have estimated the average change in A1c to be .74% with a standard deviation of 1.25% for an effect size of .59.

V. Human Subjects Protection

A. Potential Risks to Subjects

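### The 85-88% power does not follow from any effect size or SD the plan states; the target switches from .25 SD to .25% HbA1c, and equal allocation is assumed although randomisation is 2:1

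*Combined protocol and SAP*

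**What the plan says.** All in the combined protocol and SAP:

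- **Section IV, Sample Size and Power, goal:** more than 80% power for an "average difference of .25 standard deviations from baseline in HbA1c between the two groups at one year".
- **Next sentence, claim:** "With a sample size of 225 participants, we will have 85-88% power to detect a net intervention effect of .25", the last figure followed by a percent sign. A 5% loss to follow-up every six months is said to be allowed for.
- **Variance inputs:** the paragraph opens its account with "Although the DPP has not published any data that allow us to estimate the standard deviation and longitudinal correlation of HbA1c", then cites similar, longer studies that put the "average change in A1c to be .74% with a standard deviation of 1.25% for an effect size of .59". It gives no other SD and no value for the correlation.
- **Allocation in that paragraph:** participants are "randomized with equal probability to either the intensive lifestyle intervention or individual education arm".
- **Allocation in section III.E.b, Randomization:** "Randomization will occur in a 2:1 pattern; for every two participants randomized to the lifestyle intervention", one goes to usual care. About 14 of the 20-21 people in each wave go to the intervention.
- **Section IV, opening paragraph:** the main hypothesis concerns "evaluating the mean differences in changes in HbA1c at one year", tested two-sided at 0.05.
- **Section III.A:** participants have "pre-diabetes as defined by HbA1c of 5.7-6.5" per cent.

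**The concern.** Two adjacent sentences state the target on different scales, and the power attached to the second cannot be traced to any SD in the document. A reader cannot tell which effect the figure refers to or what it assumes. The paragraph also describes an allocation that the trial does not use. If the planning SD is close to the one SD quoted, 225 participants are far too few for .25% HbA1c; if it is near half of that or less, they are enough. Without the SD, the plan cannot show that a null primary result would come from an adequately powered comparison.

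**Working it through.** **Inputs.** Two-sided alpha 0.05; 225 randomised; retention to month 12 of 0.95 × 0.95 = 0.9025, so 225 × 0.9025 = 203.06 completers. That is 101.5 per arm at 1:1, or 135.4 and 67.7 at 2:1.

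**Formula.** Power for two means from the noncentral t with 201 degrees of freedom and noncentrality d / √(1/n₁ + 1/n₂), where d is the difference divided by the SD of 12-month change. The square root is 0.1404 at 1:1 and 0.1489 at 2:1.

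**Step 1: try to reproduce 85-88% from the stated inputs.**

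| Reading | d | Power, 1:1 | Power, 2:1 |
|---|---|---|---|
| .25 SD of change | 0.25 | 43% | 39% |
| .25% with SD 1.25% | 0.25/1.25 = 0.20 | 29% | 27% |
| Cited effect size | 0.74/1.25 = 0.592 | 99% | 98% |

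With no dropout at all, .25 SD gives 46% (1:1) or 42% (2:1), and .25% with SD 1.25% gives 32% or 29%. One-sided tests without dropout (normal approximation) reach at most 59% and 44% respectively. None falls in the stated range.

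**Step 2: compare the two targets.** They coincide only at an SD of 1.0%. If the SD meant is that of HbA1c at entry, screening values confined to 5.7-6.5% span 0.8%, and a variable on that range has an SD of at most 0.8/2 = 0.4%. Then .25 SD is at most 0.10%, and the targets differ by at least 0.25/0.10 = 2.5-fold.

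**Step 3: find what would give 85-88%.** The d required is 0.423-0.442 at 1:1 and 0.448-0.469 at 2:1.

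- For .25%, the SD of change must be 0.25/d: 0.592-0.565% at 1:1 and 0.558-0.533% at 2:1.
- For .25 of a cross-sectional SD with compound-symmetric levels, the mean of k changes has variance (1 − r)(1 + 1/k) in units of that SD squared. The correlation needed is therefore r = 1 − (.25/d)² / (1 + 1/k):

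| Visits averaged | r, 1:1 | r, 2:1 |
|---|---|---|
| 12 months only (k = 1) | 0.825-0.840 | 0.844-0.858 |
| 6 and 12 months (k = 2) | 0.767-0.787 | 0.793-0.811 |
| All four (k = 4) | 0.720-0.744 | 0.751-0.773 |

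The four-visit average goes beyond the one-year hypothesis.

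- If 1.25% is read as a cross-sectional SD, the SD of change is 1.25 × √(2(1 − r)). For .25%, r must be about 0.89-0.90 (1:1) or 0.90-0.91 (2:1).

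The document states none of these values.

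**Step 4: power for .25% at 2:1, by assumed SD of 12-month change.**

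| SD (%) | 0.4 | 0.5 | 0.55 | 0.6 | 0.7 | 0.8 | 1.0 | 1.25 |
|---|---|---|---|---|---|---|---|---|
| Power | 99% | 92% | 86% | 80% | 67% | 55% | 39% | 27% |

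Power is 80% at an SD of 0.63% (1:1) or 0.60% (2:1), and 50% at 0.90% (1:1) or 0.85% (2:1).

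**Step 5: effect of the allocation error alone.** At an SD of 0.6%, power falls from 84% (1:1) to 80% (2:1). If 85-88% were right at 1:1, the same assumptions would give about 81-84% at 2:1.

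**The case against.** The strongest reply is that this is an undisclosed input and not a wrong sum. Ordinary assumptions do reach the range: an SD of change near 0.57-0.59%, or a high longitudinal correlation, which the paragraph at least mentions. Quoting a range may mean that one input was varied. The narrow entry criterion also favours the protocol: if the SD were at most 0.4% at both baseline and 12 months (the second is an assumption) and the correlation not negative, the SD of change would be at most 0.4 × √2 = 0.566%, with power for .25% of at least 88% (1:1) or 84% (2:1). The 1.25% comes from longer studies and is a doubtful planning value here. The allocation conflict costs only about 4 points and on its own leaves the goal of more than 80% intact.

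Much of this stands: the trial may be well powered for .25%, and allocation is the smaller part of the problem. But every route to 85-88% needs an SD or correlation that the plan does not state, after saying that one major source could not supply either. The 0.4% limit covers screening values only; Table 3 lists HbA1c again at baseline, and nothing confines follow-up values. If 1.25% is not the planning SD, the plan has none.

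Two points on detail. The four-visit correlations use 12-month retention, but the model keeps participants with incomplete visits, and the stated loss rate leaves the equivalent of about 207 full records before late entrants are cut short, close to the 203 used. All figures treat participants as independent, although the lifestyle arm meets in 11 groups. With an assumed intraclass correlation of 0.01 or 0.05 in that arm only, 80% power at 2:1 would fall to about 78% or 73%.

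**Conclusion.** The concern holds. As written, the 85-88% is not delivered by the paragraph's own inputs: these give 43% or 29% at the allocation it describes and 39% or 27% at the allocation used, while the cited effect size gives 98-99%. The target is stated on two scales that are not equivalent, and equal allocation contradicts section III.E.b. This makes the stated power unsupported; it does not show the trial to be too small. At 2:1, power for .25% is 80% or more only if the SD of 12-month change is about 0.60% or less, and it drops below 50% only above about 0.85%. These figures assume two-sided 0.05, about 203 completers, a 12-month comparison and independent participants. Because this is the sole justification of the sample size for the primary outcome, it must be corrected.

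**What to change.** Rewrite the Sample Size and Power paragraph so that it:

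1. gives one target in one unit;
2. states the assumed SD of 12-month change and its source, and, if a repeated-measures gain is claimed, the correlation, the visits and the model behind it;
3. computes power at 2:1;
4. says whether participants are treated as independent within the lifestyle groups.

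Possible text: *With 225 participants randomised 2:1 and about 10% lost by month 12 (about 135 and 68 analysed, treated as independent), the trial has 80% power for a difference of 0.42 SD of 12-month change in HbA1c. Power for a difference of 0.25% HbA1c is about 99%, 80%, 55% and 27% if the SD of change is 0.4%, 0.6%, 0.8% and 1.25%.*

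Remove the 85-88% figure, the aim of more than 80% power for .25 SD, and the statement of equal allocation. Either power statement could stay only if the SD and correlation that support it are given and it is recomputed at 2:1.

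The cost is protocol wording. Stated power becomes conditional on an SD and may look less favourable. No extra enrolment and no change to the analysis is proposed.

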Appendix B. La Comunidad Baseline and Follow-Up Questionnaires

Physical Activity Readiness Questionnaire (PAR-Q)

Becoming more active is very safe for most people, but just to be certain, please complete the questionnaire below. Some people should check with their doctor before they start becoming much more physically active. Start by answering the seven questions below.

1. Has your doctor ever said that you have a heart condition and that you should only do physical activity recommended by a doctor?
 YES NO
2. Do you feel pain in your chest when you do physical activity?
 YES NO
3. In the past month, have you had chest pain when you were not doing physical activity?
 YES NO
4. Do you lose your balance because of dizziness or do you ever lose consciousness?
 YES NO
5. Do you have a bone or joint problem that could be made worse by a change in your physical activity?
 YES NO
6. Is your doctor currently prescribing drugs (for example, water pills) for your blood pressure or heart condition?
 YES NO
7. Do you know of any other reason why you should not do physical activity?
 YES NO

If you answered YES to one or more questions, talk with your doctor before you start becoming much more physically active.

If you answered NO to all questions, you can be reasonably sure that you can start becoming more physically active right now. Be sure to start slowly and progress gradually- this is the safest and easiest way to go.

Referred to primary care physician for medical clearance prior to participation

CURRENT PHYSICAL ACTIVITY LEVEL

VIGOROUS PHYSICAL ACTIVITY

First we are going to ask you some questions about your participation in vigorous or "hard" activities. These are activities that take hard physical effort, make you breathe much harder than normal, and cause heavy sweating.

1. In general how many days per week do you do vigorous activities like running, heavy lifting, aerobics, or fast bicycling for at least 10 minutes in a row? Do not count any vigorous activities you did for less than 10 minutes in a row. Assume that one week is seven (7) days.

CHECK ONLY ONE ANSWER

0 Days per week	4 Days per week
1 Day per week	5 Days per week
2 Days per week	6 Days per week
3 Days per week	7 Days per week

2. On the days that you do vigorous activities, how much time do you usually spend doing them? Only count the time that you spend doing vigorous activity *for at least 10 minutes in a row*. **CHECK ONLY ONE ANSWER**

- I do not do vigorous activity for more than 10 minutes in a row
- 10-15 minutes per day
- 15-30 minutes per day
- 30-45 minutes per day
- 45-60 minutes per day
- Over 60 minutes per day

DAILY WALKING

Next we are going to ask you about your daily walking.

3. In general, how many days per week do you walk *for at least 10 minutes in a row?*
Think about all the walking you do during the day, including walking for exercise, walking to get to places (transportation), walking at work or home, or any other walking that you do during the day. Do not count any walking that you do for less than 10 minutes in a row. **CHECK ONLY ONE ANSWER**

0 Days per week	4 Days per week
1 Day per week	5 Days per week
2 Days per week	6 Days per week
3 Days per week	7 Days per week

4. On the days that you walk, how much time do you usually spend walking? Only count the time that you spend walking *for at least 10 minutes in a row.* **CHECK ONLY ONE ANSWER**

- I do not walk for more than 10 minutes in a row
- 10-15 minutes per day
- 15-30 minutes per day
- 30-45 minutes per day
- 45-60 minutes per day
- Over 60 minutes per day

5. Of the time you spend walking *for at least 10 minutes in a row*, how much of that time is spent in brisk walking that increases your heart rate and breathing faster than normal?

CHECK ONLY ONE ANSWER

- I do not walk briskly for more than 10 minutes in a row
- 10-15 minutes per day
- 15-30 minutes per day
- 30-45 minutes per day
- 45-60 minutes per day
- Over 60 minutes per day

OTHER MODERATE PHYSICAL ACTIVITY

Last, we are going to ask you about your participation in moderate activities other than walking. These are activities that take some physical effort, and increase your heart rate and breathing above resting levels, but is not as hard as vigorous activity. Please **do not include walking** in any of your answers about moderate activity.

6. In general, how many days per week do you do moderate activities like carrying light loads, playing doubles tennis, or regular bicycling, *for at least 10 minutes in a row*. Assume that one week is seven (7) days. **CHECK ONLY ONE ANSWER**

0 Days per week	4 Days per week
1 Day per week	5 Days per week
2 Days per week	6 Days per week
3 Days per week	7 Days per week

7. On the days that you do other moderate activities, how much time do you usually spend doing them? Only count the time that you spend doing moderate activity *for at least 10 minutes in a row*. **CHECK ONLY ONE ANSWER**

- I do not do moderate activity for more than 10 minutes in a row
- 10-15 minutes per day
- 15-30 minutes per day
- 30-45 minutes per day
- 45-60 minutes per day
- Over 60 minutes per day

ARE YOU AT RISK FOR

TYPE 2 DIABETES?

Diabetes Risk Test

1 How old are you?

Less than 40 years (0 points)
40–49 years (1 point)
50–59 years (2 points)
60 years or older (3 points)

Write your score
in the box.

2 Are you a man or a woman?

Man (1 point) Woman (0 points)

3 If you are a woman, have you ever been diagnosed with gestational diabetes?

Yes (1 point) No (0 points)

4 Do you have a mother, father, sister, or brother with diabetes?

Yes (1 point) No (0 points)

5 Have you ever been diagnosed with high blood pressure?

Yes (1 point) No (0 points)

6 Are you physically active?

Yes (0 points) No (1 point)

7 What is your weight status?
(see chart at right)

Add up
your score.

If you scored 5 or higher:

You are at increased risk for having type 2 diabetes. However, only your doctor can tell for sure if you do have type 2 diabetes or prediabetes (a condition that precedes type 2 diabetes in which blood glucose levels are higher than normal). Talk to your doctor to see if additional testing is needed.

Type 2 diabetes is more common in African Americans, Hispanics/Latinos, American Indians, and Asian Americans and Pacific Islanders.

For more information, visit us at
www.diabetes.org or call [name]

Visit us on Facebook
Facebook.com/AmericanDiabetesAssociation

Height	Weight (lbs.)	
4'10"	119-142	143-190
4'11"	124-147	148-197
5' 0"	128-152	153-203
5' 1"	132-157	158-210
5' 2"	136-163	164-217
5' 3"	141-168	169-224
5' 4"	145-173	174-231
5' 5"	150-179	180-239
5' 6"	155-185	185-246
5' 7"	159-190	191-254
5' 8"	164-196	197-261
5' 9"	169-202	203-269
5' 10"	174-208	209-277
5' 11"	179-214	215-285
6' 0"	184-220	221-293
6' 1"	189-226	227-301
6' 2"	194-232	233-310
6' 3"	200-239	240-318
6' 4"	205-245	246-327
	(1 Point)	(2 Points)
	(3 Points)	

You weigh less than the amount
in the left column
(0 points)

Adapted from Bang et al., Ann Intern Med 151:775-782, 2009.

Original algorithm was validated without gestational diabetes as part of the model.

Lower Your Risk

The good news is that you can manage your risk for type 2 diabetes. Small steps make a big difference and can help you live a longer, healthier life.

If you are at high risk, your first step is to see your doctor to see if additional testing is needed.

Visit diabetes.org or call [name] for information, tips on getting started, and ideas for simple, small steps you can take to help lower your risk.

Barriers to Physical Activity

The items below reflect common reasons preventing people from participating in exercise sessions or, in some cases, for dropping out or quitting exercise altogether. Please indicate how confident you are that you could exercise in the event that any of the following circumstances were to occur.

1. How confident are you that you could maintain your physical activity if you were **tired**?

									
1	2	3	4	5	6	7	8	9	10
No Confidence	Moderate Confidence				Complete Confidence				

2. How confident are you that you could maintain your physical activity **during or following a personal crisis**?

									
1	2	3	4	5	6	7	8	9	10
No Confidence	Moderate Confidence				Complete Confidence				

3. How confident are you that you could maintain your physical activity **during bad weather**?

									
1	2	3	4	5	6	7	8	9	10
No Confidence	Moderate Confidence				Complete Confidence				

5. How confident are you that you could maintain your physical activity **when you are on vacation**?

									
1	2	3	4	5	6	7	8	9	10
No Confidence	Moderate Confidence				Complete Confidence				

6. How confident are you that you could maintain your physical activity **when you have other competing interests** (like your favorite TV show)?

									
1	2	3	4	5	6	7	8	9	10
No Confidence	Moderate Confidence				Complete Confidence				

7. How confident are you that you could maintain your physical activity when **you have a lot of work to do?**

									
1	2	3	4	5	6	7	8	9	10
No Confidence	Moderate Confidence					Complete Confidence			

8. How confident are you that you could maintain your physical activity if you had to do it **by yourself?**

									
1	2	3	4	5	6	7	8	9	10
No Confidence	Moderate Confidence					Complete Confidence			

9. How confident are you that you could maintain your physical activity if you were **recovering from an illness?**

									
1	2	3	4	5	6	7	8	9	10
No Confidence	Moderate Confidence					Complete Confidence			

10. How confident are you that you could maintain your physical activity **when your schedule is hectic?**

									
1	2	3	4	5	6	7	8	9	10
No Confidence	Moderate Confidence					Complete Confidence			

How confident are you that you could lose...

1. 5% of your body weight (XX pounds) and keep it off
 
 
 	
 
 1	2	3	4	5	6	7	8	9	10	
 
 No Confidence	Moderate Confidence	Complete Confidence	
 
											1	2	3	4	5	6	7	8	9	10	No Confidence	Moderate Confidence				Complete Confidence													
																																							
1	2	3	4	5	6	7	8	9	10																														
No Confidence	Moderate Confidence				Complete Confidence																																		

2. 7½% of your body weight (XX pounds) and keep it off
 
 
 	
 
 1	2	3	4	5	6	7	8	9	10	
 
 No Confidence	Moderate Confidence	Complete Confidence	
 
											1	2	3	4	5	6	7	8	9	10	No Confidence	Moderate Confidence				Complete Confidence													
																																							
1	2	3	4	5	6	7	8	9	10																														
No Confidence	Moderate Confidence				Complete Confidence																																		

3. 10% of your body weight (XX pounds) and keep it off
 
 
 	
 
 1	2	3	4	5	6	7	8	9	10	
 
 No Confidence	Moderate Confidence	Complete Confidence	
 
											1	2	3	4	5	6	7	8	9	10	No Confidence	Moderate Confidence				Complete Confidence													
																																							
1	2	3	4	5	6	7	8	9	10																														
No Confidence	Moderate Confidence				Complete Confidence																																		

4. 12½% of your body weight (XX pounds) and keep it off
 
 
 	
 
 1	2	3	4	5	6	7	8	9	10	
 
 No Confidence	Moderate Confidence	Complete Confidence	
 
											1	2	3	4	5	6	7	8	9	10	No Confidence	Moderate Confidence				Complete Confidence													
																																							
1	2	3	4	5	6	7	8	9	10																														
No Confidence	Moderate Confidence				Complete Confidence																																		

5. 15% of your body weight (XX pounds) and keep it off
 
 
 	
 
 1	2	3	4	5	6	7	8	9	10	
 
 No Confidence	Moderate Confidence	Complete Confidence	
 
											1	2	3	4	5	6	7	8	9	10	No Confidence	Moderate Confidence				Complete Confidence													
																																							
1	2	3	4	5	6	7	8	9	10																														
No Confidence	Moderate Confidence				Complete Confidence																																		

Please tell your current desire to be able to perform each task. Please respond using a range of 0 (no desire whatsoever) to 4 (very strong desire). **It is very important to remember that we are not interested in whether you can do the tasks or not; rather, we are interested in your level of desire to be able to do each task.**

Please rate your level of desire to be able to...

1. Exercise at a moderate intensity for 10 minutes.				
				
0 No Desire Whatsoever	1 Low Desire	2 Moderate Desire	3 Strong Desire	4 Very Strong Desire
2. Exercise at a moderate intensity for 20 minutes.				
				
0 No Desire Whatsoever	1 Low Desire	2 Moderate Desire	3 Strong Desire	4 Very Strong Desire
3. Exercise at a moderate intensity for 30 minutes.				
				
0 No Desire Whatsoever	1 Low Desire	2 Moderate Desire	3 Strong Desire	4 Very Strong Desire
4. Exercise at a moderate intensity for 40 minutes.				
				
0 No Desire Whatsoever	1 Low Desire	2 Moderate Desire	3 Strong Desire	4 Very Strong Desire
5. Exercise at a moderate intensity for 50 minutes.				
				
0 No Desire Whatsoever	1 Low Desire	2 Moderate Desire	3 Strong Desire	4 Very Strong Desire
6. Exercise at a moderate intensity for 60 minutes.				
				
0 No Desire Whatsoever	1 Low Desire	2 Moderate Desire	3 Strong Desire	4 Very Strong Desire

Please indicate below how confident you are that you can successfully carry out each of the following activities.

"I BELIEVE THAT I COULD EXERCISE..."

1. For 10 minutes at a moderate intensity without stopping?									
									
1	2	3	4	5	6	7	8	9	10
No Confidence	Moderate Confidence					Complete Confidence			
2. For 20 minutes at a moderate intensity without stopping									
									
1	2	3	4	5	6	7	8	9	10
No Confidence	Moderate Confidence					Complete Confidence			
3. For 30 minutes at a moderate intensity without stopping									
									
1	2	3	4	5	6	7	8	9	10
No Confidence	Moderate Confidence					Complete Confidence			
4. For 40 minutes at a moderate intensity without stopping									
									
1	2	3	4	5	6	7	8	9	10
No Confidence	Moderate Confidence					Complete Confidence			
5. For 50 minutes at a moderate intensity without stopping									
									
1	2	3	4	5	6	7	8	9	10
No Confidence	Moderate Confidence					Complete Confidence			
6. For 60 minutes at a moderate intensity without stopping									
									
1	2	3	4	5	6	7	8	9	10
No Confidence	Moderate Confidence					Complete Confidence			

This questionnaire relates to eating. Please respond to each statement by indicating how confident you are that you can resist or control your eating in the following situations by placing a check mark in the appropriate box.

1. I can resist eating when I am anxious (nervous).

0 1 2 3 4 5 6 7 8 9

NOT AT ALL
CONFIDENT

MODERATELY
CONFIDENT

VERY
CONFIDENT

2. I can control my eating on the weekends.

0 1 2 3 4 5 6 7 8 9

NOT AT ALL
CONFIDENT

MODERATELY
CONFIDENT

VERY
CONFIDENT

3. I can resist eating even when I have to say "no" to others.

0 1 2 3 4 5 6 7 8 9

NOT AT ALL
CONFIDENT

MODERATELY
CONFIDENT

VERY
CONFIDENT

4. I can resist eating when I feel physically run down.

0 1 2 3 4 5 6 7 8 9

NOT AT ALL
CONFIDENT

MODERATELY
CONFIDENT

VERY
CONFIDENT

5. I can resist eating when I am watching TV.

0	1	2	3	4	5	6	7	8	9
									
NOT AT ALL	MODERATELY					VERY			
CONFIDENT	CONFIDENT					CONFIDENT			

6. I can resist eating when I am depressed (or down).

0	1	2	3	4	5	6	7	8	9
									
NOT AT ALL	MODERATELY					VERY			
CONFIDENT	CONFIDENT					CONFIDENT			

7. I can resist eating when there are many different kinds of food available.

0	1	2	3	4	5	6	7	8	9
									
NOT AT ALL	MODERATELY					VERY			
CONFIDENT	CONFIDENT					CONFIDENT			

8. I can resist eating even when I feel it's impolite to refuse a second helping.

0	1	2	3	4	5	6	7	8	9
									
NOT AT ALL	MODERATELY					VERY			
CONFIDENT	CONFIDENT					CONFIDENT			

9. I can resist eating even when I have a headache.

0	1	2	3	4	5	6	7	8	9
									
NOT AT ALL	MODERATELY					VERY			
CONFIDENT	CONFIDENT					CONFIDENT			

10. I can resist eating when I am reading.

0	1	2	3	4	5	6	7	8	9
									
NOT AT ALL	MODERATELY					VERY			
CONFIDENT	CONFIDENT					CONFIDENT			

11. I can resist eating when I am angry (or irritable).

0	1	2	3	4	5	6	7	8	9
									
NOT AT ALL	MODERATELY					VERY			
CONFIDENT	CONFIDENT					CONFIDENT			

12. I can resist eating even when I am at a party.

0	1	2	3	4	5	6	7	8	9
									
NOT AT ALL	MODERATELY					VERY			
CONFIDENT	CONFIDENT					CONFIDENT			

13. I can resist eating even when others are pressuring me to eat.

0	1	2	3	4	5	6	7	8	9
									
NOT AT ALL	MODERATELY					VERY			
CONFIDENT	CONFIDENT					CONFIDENT			

14. I can resist eating when I am in pain.

0	1	2	3	4	5	6	7	8	9
									
NOT AT ALL	MODERATELY					VERY			
CONFIDENT	CONFIDENT					CONFIDENT			

15. I can resist eating just before going to bed.

0	1	2	3	4	5	6	7	8	9
									
NOT AT ALL	MODERATELY					VERY			
CONFIDENT	CONFIDENT					CONFIDENT			

16. I can resist eating when I have experienced failure.

0	1	2	3	4	5	6	7	8	9
									
NOT AT ALL	MODERATELY					VERY			
CONFIDENT	CONFIDENT					CONFIDENT			

17. I can resist eating even when high-calorie foods are available.

0	1	2	3	4	5	6	7	8	9
									
NOT AT ALL	MODERATELY					VERY			
CONFIDENT	CONFIDENT					CONFIDENT			

18. I can resist eating even when I think others will be upset if I don't eat.

0	1	2	3	4	5	6	7	8	9
									
NOT AT ALL	MODERATELY					VERY			
CONFIDENT	CONFIDENT					CONFIDENT			

19. I can resist eating when I feel uncomfortable.

0	1	2	3	4	5	6	7	8	9
									
NOT AT ALL	MODERATELY					VERY			
CONFIDENT	CONFIDENT					CONFIDENT			

20. I can resist eating when I am happy.

0	1	2	3	4	5	6	7	8	9
									
NOT AT ALL	MODERATELY					VERY			
CONFIDENT	CONFIDENT					CONFIDENT			

MY HEALTH BEHAVIORS

Tobacco Use

[figure not shown]
1. Have you smoked at least 100 cigarettes during your entire life?

Yes

No *go to Question 9, next page*

2. Do you smoke cigarettes now?

Yes

About how old were you when you first started smoking cigarettes (fairly regu)

Age

No

go to Question 7, below

3. Do you now smoke cigarettes every day or some days?

Every Day

Some

4. On how many of the past 30 days did you smoke cigarettes?

	
--------------------------	--------------------------

Number of days

5. On the days that you smoke, about how many cigarettes do you usually smoke per day?

	
--------------------------	--------------------------

Number of cigarettes per day

6. For approximately how many years have you smoked this amount?

	
--------------------------	--------------------------

Number of years

go to Question 9, next page

7. About how old were you when you quit smoking cigarettes (fairly regularly)?

	
--------------------------	--------------------------

Age

a. About how old were you when you first started smoking cigarettes (fairly regularly)?

	
----------------------	----------------------

Age

8. About how many cigarettes per day did you usually smoke at that time?

	
----------------------	----------------------

Number of cigarettes per day

9. Does anyone living with you now smoke cigarettes regularly inside your home?

¹ Yes

² No ***go to Section B, "Alcohol Use," below***

a. Please mark all the people who live with you who now smoke cigarettes regularly inside your home: Mark all that apply.

¹ Spouse or partner ² Son(s) or daughter(s) ³ Other person/people

Alcohol Use

1. Did you drink any alcoholic beverages in the past year?

¹ Yes ***Go to Question 2, below***

² No ***go to Section C, "Eating Patterns," next page***

2. How many drinks of wine do you usually have per week? By drink, we mean about a 5-ounce

glass.

	
----------------------	----------------------

Drinks per week

3. How many drinks of beer do you usually have per week? One beer is a 12-ounce glass, can, or

bottle.

	
----------------------	----------------------

Drinks per week

4. How many drinks of liquor do you usually have per week? Count each shot (1 ½ ounces) as one

drink.

	
----------------------	----------------------

Drinks per week

5. During the past 24 hours, how many drinks have you had?

	
----------------------	----------------------

Drinks

6. In the past month, what is the largest number of drinks you had in one day?

	
----------------------	----------------------

Drinks

7. Have you made any attempts to stop drinking in the past five years?

¹ Yes

² No

8. During the past 30 days, on how many days did you have five or more drinks on the same occasion?

By "occasion," we mean at the same time or within a couple of hours of each other.

	
----------------------	----------------------

Days

Eating Patterns

1. How many days out of the 7-day week do you eat breakfast?

	
----------------------	----------------------

Days per week

2. How many days out of the 7-day week do you eat lunch/brunch?

	
----------------------	----------------------

Days per week

3. How many days out of the 7-day week do you eat dinner?

	
----------------------	----------------------

Days per week

4. Counting all meals and any snacks you may have, how many times a day do you usually eat:

	
----------------------	----------------------

Times per day

5. How many days a week do you eat out at...	Breakfast	Brunch/Lunch	
Dinner			
a. Fast food restaurants for:	days/wk	days/wk	days/wk
b. Other types of restaurants for:			
	days/wk	days/wk	days/wk
6. In the past 6 months, have you experienced any food cravings (i.e., intense desires to eat a specific food)?			
¹  Yes			
²  No			

Weight Control Practices

1. How often do you weigh yourself? (check one answer only)

- ¹ Never
- ² About once a year or less
- ³ Every couple of months
- ⁴ Every month
- ⁵ Every week
- ⁶ Every day
- ⁷ More than once per day

Myself and My Family

MYSELF

1. Marital Status: (Choose one that is most appropriate)

 1 Never married	 4 Widowed
 2 Married	 5 Separated
 3 Divorced	 6 Living in a marriage-like relationship

2. What is the most education you have completed?

CHECK ONLY ONE BOX FOR THE HIGHEST LEVEL OF SCHOOLING YOU RECEIVED.

 1 Less than high school
 2 High-school diploma or equivalency (GED)
